COPD is associated with high mortality and morbidity. Hospitalizations for acute exacerbations of COPD account for a relatively large proportion of annual direct costs for COPD (3). Furthermore, one in five patients is estimated to require re-hospitalization within 30 days of discharge after an admission for acute exacerbation, indicating a lack of effectiveness of standard treatment to prevent future exacerbations in a substantial proportion of COPD patients (3). A high blood eosinophil count may be a biomarker to identify these patients and may be useful to determine the most appropriate treatment for people with COPD. Blood eosinophils may help to identify patients who may benefit from ICS treatment (4) and who are at risk of exacerbations if ICS are withdrawn (5) and to direct treatment for exacerbations (6).

COPD prescription costs are high and rising and often inappropriate (2). Thus, there is a need for understanding who are high resource patients and how to identify them.

To our knowledge there is no information available on the burden and cost of COPD in patients with high blood eosinophil counts who are at risk of exacerbations despite receiving treatment with triple therapy.

This study aims to evaluate the role of high blood eosinophil counts measured during stable disease in the burden and costs of COPD in a broad real-life population of patients in the UK.

Objectives:

Observational historical follow-up studies investigating the role of blood eosinophils in the burden and costs of COPD with the following objectives:

1. To study the association between high blood eosinophil counts at the time of stable COPD (i.e., no recent exacerbation and stable treatment during the study period) and the prospective exacerbation rate in different subgroups of patients with COPD defined by treatment regimen and smoking habits and to study whether this association is also found in patients with good adherence to ICS
2. To study whether patients admitted to hospital for COPD exacerbation are more likely to be re-admitted if their pre-admission eosinophil count (assessed at the time when there was no recent exacerbation) is high
3. A. To estimate mean all-cause and COPD-related health care resource use (HRU) and associated costs in 4 subgroups of patients who are at risk of exacerbations (i.e. a history of ≥ 2 exacerbations or ≥ 1 exacerbation leading to hospitalisation in the past 12 months) while receiving treatment with triple therapy, where the 4 subgroups are defined by the presence or absence of high blood eosinophil counts and current smoking habits
B. to compare HRU and costs with those for the total population of patients with COPD who have blood eosinophil counts available
4. To study whether the presence of high blood eosinophil counts is associated with greater all-cause and COPD-related costs in the subsequent year and to study which other easily accessible characteristics drive future costs in patients with COPD

Methods:

Study design:

An observational historical cohort study will be performed among the UK population of patients with COPD who have blood eosinophil counts available.

Patients will be characterised in a baseline year prior to the index date (ID) and outcomes will be measured in the year after ID.

Data Sources:

Analyses for sub-study 1 (association between high eosinophil counts and COPD exacerbations) will be performed in patients from OPCR. A subpopulation of patients from CPRD with linkage to Hospital Episode Statistics (HES) available will be selected for sub-studies 2–4 (association between high blood eosinophil counts and the risk of hospital re-admission for COPD and study on HRU and costs)

Study Population:

The index date (ID) will be the most recent blood eosinophil count measurement, except for sub-study 2 for which the hospital discharge date of the most recent first hospitalization for COPD within one year after a blood eosinophil count measurement will be used as ID. Eligible patients should be ≥ 40 years old and have at least 1 year of continuous data prior to and after the respective IDs, except for sub-study 2 in which patients who die or who are lost to follow-up in the outcome year are censored. Patients eligible for sub-study 1 need to be on stable treatment during the study period.

Exposures:

Only eosinophil counts measured when there was no recent (4 weeks) exacerbation recorded are considered. The primary definition of high blood eosinophil counts will be $\geq 0.45 \times 10^9/L$, based on previous work. Sensitivity analyses will be performed using ≥ 0.25 , ≥ 0.35 and $\geq 0.55 \times 10^9/L$ as the definition.

Outcomes:

The primary outcome measure for objective 1 will be the number of COPD exacerbations during the outcome year. The number of oral steroids courses will be analysed as secondary outcome.

The occurrence of a re-admission to hospital with COPD exacerbation at any diagnostic position within 4 weeks, 12 weeks and 1 year after discharge from hospital will be the primary outcome measure for objective 2.

HRU and costs will be outcomes for objectives 3 and 4.

Sample Size Estimations:

For objective 1, a total of 1,645 patients are required for each therapy group to find a significant ($\alpha=0.05$) Rate Ratio of 1.3 as previously found with 80% power, when analysing the association between high blood eosinophil counts and the number of exacerbations, assuming 10% of patients having high blood eosinophil counts and a mean rate of events of 0.68 in patients without high blood eosinophil as found in a previous study conducted by OPRI.

For objective 2, around 10,000 patients hospitalized for COPD with a blood eosinophil count available within one year prior to ID are required for finding a hazard ratio of 1.3 for the association between a high blood eosinophil count and re-admission risk, assuming a re-admission risk of 10% within 4 weeks in patients with normal eosinophil counts.

For objective 3, a total number of 980 patients with ≥ 2 exacerbations in the baseline year while receiving triple therapy are required to find a 0.3 standard deviation greater

amount of (the logarithm) of total costs in patients with high blood eosinophil counts compared with patients with normal counts.

For objective 4, a total number of 2,200 patients are required for finding a significant difference of 0.2 standard deviations between the means of (the logarithm) of total costs of patient groups with and without high blood eosinophil counts.

Statistical Analysis:

Negative binomial regression will be performed to estimate Rate Ratios with 95% confidence intervals (CI) for the association between high blood eosinophil counts and the number of COPD exacerbations in the outcome year, stratified by different treatment options and current smoking habits, adjusted for potential confounders assessed at baseline.

Analyses will be performed in patients on different treatment regimens, adjusted for potential confounders (see paragraph 3.3.2) in two populations:

1. The full population of patients with COPD
2. A subpopulation of patients with "classical COPD" who had $FEV_1/FVC < 0.70$ recorded within 5 years prior to the index date, never received an asthma diagnosis and have a smoking history

Whether the association is modified by the Medication Possession Ratio (MPR) for ICS in the baseline year will be studied by including an interaction term of eosinophil count and MPR into the regression model and by repeating the analyses in patients adherent to treatment ($MPR \geq 80\%$).

Risks of re-admission to hospital for COPD will be reported in a life-table and Kaplan-Meier curves will be constructed for patients with and without high eosinophil counts within 4 and 12 weeks and 1 year after hospital discharge. Comparisons will be made with the use of a log-rank analysis. Cox-proportional hazard regression with the time from hospital discharge date to the first re-admission date as time to event will be performed to estimate Hazard Ratios with 95% CI for the association between high eosinophil counts and time to re-admission, adjusted for potential confounders.

HRU and costs will be described in the baseline and outcome years. Mean costs with standard deviations will be estimated for subgroups of patients based on reference costs published by the UK National Health Service (NHS). Cost ratios with 95% CI will be estimated for comparison of costs with the overall mean in the total population of patients with COPD.

A one- or two-step generalized linear model with gamma distribution and log link will be used to perform regression analysis with total costs as the outcome variable.

All candidate predictors will be fed into a multiple regression analysis with backwards selection of the model with the best fit based on Akaike's information criterion (AIC).

An interaction term of blood eosinophil counts and smoking status will be included in the model as potential predictor next to the main effects to evaluate relevant modification of the independent effect of blood eosinophil counts by different smoking habits. Relative costs will be estimated from the model for patients with and without high blood eosinophil counts.

AMENDMENT HISTORY

Date	Brief description of change	Administrative Change / Amendment / New Protocol Version.
11 October 2016	First draft protocol for AZ review	V1.0
31 October 2016	Revised draft protocol after AZ review	V2.0
18 November 2016	Revision following comments SC	V3.0

MILESTONES

Date	Milestone
11 November 2016	Final protocol and statistical analysis plan
16 December 2016	Delivery report sub-study 1: association between high blood eosinophil counts and COPD exacerbations rates
23 December 2016	Delivery report sub-study 2: association between high blood eosinophil counts and hospital re-admission rates
23 January 2017	Delivery report sub-study 3: HRU and costs in subgroups of COPD patients
6 March 2017	Manuscript submission sub-studies 1 & 2
16 March 2017	Delivery report sub-study 4: patient's characteristics that drive future all-cause and COPD-related costs
6 July 2017	Manuscript submission sub-studies 3 & 4

1. BACKGROUND AND RATIONALE

1.1 Background

In the UK, 4.5% of all people aged over 40 are estimated to live with diagnosed Chronic Obstructive Pulmonary Disease (COPD), based on Read codes recorded in Electronic Medical Records (7). The UK is among the top 20 countries for COPD mortality worldwide (8).

COPD is a heterogeneous condition with patients showing varying clinical and pathophysiological features. The identification of COPD phenotypes with distinct characteristics may allow targeted treatment strategies directed towards specific biological pathways.

Eosinophilic inflammation is thought to be a characteristic feature of asthma rather than COPD. However, studies have shown that there is a subset of COPD patients with eosinophilic airway inflammation, even after exclusion of patients with any features of asthma (1). Interestingly, this subset of patients with COPD exhibit the greatest response to corticosteroid treatment (4, 9) and tailoring of therapy based on sputum eosinophil counts is more effective in reducing exacerbations than treatment according to traditional guidelines (5). This suggests that there is a sub-phenotype of COPD with an eosinophilic type of airway inflammation similar to that observed in patients with asthma (10).

In a study performed in patients with COPD from the general population of Denmark, blood eosinophil levels above $0.34 \times 10^9 / L$ were associated with a 1.76-fold increased risk for severe COPD exacerbations requiring hospitalization and with a 1.15-fold increased risk for exacerbations not requiring hospital admission (11).

Previous work conducted at OPRI confirmed the increased risk of exacerbations with high blood eosinophil counts in real-life UK patients with COPD from the Optimum Patient Care Research Database (OPCRD) when using a higher cut-point of $\geq 0.45 \times 10^9 / L$, observed in 10% of the population (submitted for publication). However, the association was limited to patients who were not actively smoking. Ex-smokers with high blood eosinophil counts showed a 32% higher rate of exacerbations than ex-smokers with normal eosinophil counts. The association was found in patients treated with ICS and in patients in GOLD groups B to D, and was not influenced by any prior recording of asthma.

[figure not shown]
To date, guidelines mention that no treatment has been shown to influence the accelerated decline in lung function that is characteristic of COPD, highlighting the limited treatment options for this patient population (12). Post-hoc analyses of trial data suggest that patients with high blood eosinophil counts may benefit from inhaled corticosteroids (ICS) treatment in terms of a lower rate of decline in FEV₁ (13), but this requires confirmation in specifically designed studies. Both NICE and GOLD strategy documents recommend the use of ICS as part of a fixed dose combination (FDC) ICS/LABA treatment for patients who have 2 or more exacerbations per year or moderate to severe airflow limitation (FEV₁ <50% predicted normal) (GOLD groups C and D) (Figure 1). Most ICS/LABA combinations are indicated for symptomatic treatment of patients with COPD with FEV₁ $\leq 70\%$ predicted.

However, there is an increasing body of evidence suggesting a link between treatment with

high doses of ICS and the risk of comorbidities, such as cataracts, osteoporosis and pneumonia events, clearly associated with systemic/oral corticosteroids (14-17).

Despite these guidelines, real-world studies indicate that pharmacological treatments often differ from the recommendations. ICS is frequently prescribed to patients with less severe COPD (2). This may reflect the heterogeneity of COPD with different treatment effects of ICS in different subgroups of patients with COPD.

Algorithm showing use of inhaled therapies.

John O'Reilly, and Michael Rudolf Thorax 2011;66:93-96

Figure 1. COPD Therapy guidelines by NICE (16).

COPD is associated with high mortality and morbidity. Hospitalizations for acute exacerbations of COPD account for a relatively large proportion of annual direct costs for COPD (3). Furthermore, one in five patients is estimated to require re-hospitalization within 30 days of discharge after an admission for acute exacerbation, indicating a lack of effectiveness of standard treatment to prevent future exacerbations in a substantial proportion of COPD patients (3). A recent study found that patients with relatively low blood eosinophil counts ($\leq 2\%$) and high CRP levels measured at exacerbation had higher re-admission rates during 6 months of follow up than eosinophilic patients (18). However, low blood eosinophil

counts during exacerbations are a marker of bacterial infection (19), which does not exclude high blood eosinophil counts at the time of stable disease to be a risk factor of COPD re-admission after therapy failure.

There is sparse evidence available that high blood eosinophil counts present at the time of stable disease are associated with increased all-cause mortality during long-term follow-up (20).

This study aims to evaluate the role of high blood eosinophil counts measured during stable disease in the burden and costs of COPD in a broad real-life population of patients in the UK.

1.2 Rationale

Previous work conducted at OPRI found an increased risk of exacerbations with high blood eosinophil counts. However, the role of different treatment regimens in the association between blood eosinophil count and COPD exacerbations needs to be further elucidated. It is unknown whether the association is also present in the subgroup of patients with COPD who are adherent to ICS and in patients on triple therapy, to which one third of UK patients with COPD progresses in real life (2).

It is also unknown whether patients who have high blood eosinophil counts at the time of stable disease and who experience an exacerbation that requires hospitalization have an increased risk of short-term recurrence of exacerbations and re-admission to hospital.

To our knowledge there is no information available on the burden and cost of COPD in patients on triple therapy who have high blood eosinophil counts and experience frequent exacerbations.

1.3 Hypotheses

A high blood eosinophil count present at the time of no exacerbation is a biomarker identifying a phenotype of COPD associated with an increased rate of exacerbations at all levels of treatment in patients who are not actively smoking. High blood eosinophil counts are associated with an increased risk of short-term re-admission to hospital for COPD exacerbation.

Medical costs associated with COPD are meaningfully higher in patients with high blood eosinophil counts than in patients with normal counts.

Especially the subgroup of patients with COPD on triple therapy who have high blood eosinophil counts and are at risk of exacerbation account for high future health care resource use (HRU) and associated costs.

1.4 Objectives

1. To study the association between high blood eosinophil counts at the time of stable COPD (i.e., no recent exacerbation and stable treatment during the study period) and the prospective exacerbation rate in different subgroups of patients with COPD defined by treatment regimen and smoking habits and to study whether this association is also found in patients with good adherence to ICS
2. To study whether patients admitted to hospital for COPD exacerbation are more likely to be re-admitted if their pre-admission eosinophil count (assessed at the time when there was no recent exacerbation) is high
3. A. To estimate mean all-cause and COPD-related health care resource use (HRU) and associated costs in 4 subgroups of patients who are at risk of exacerbations (i.e. a history of ≥ 2 exacerbations or ≥ 1 exacerbation leading to hospitalisation in the past 12 months) while receiving treatment with triple therapy, where the 4 subgroups are defined by the presence or absence of high blood eosinophil counts and current smoking habits
B. to compare HRU and costs with those for the total population of patients with COPD who have blood eosinophil counts available
4. To study whether the presence of high blood eosinophil counts is associated with greater all-cause and COPD-related costs in the subsequent year and to study which other easily accessible characteristics drive future costs in patients with COPD

2. METHODOLOGY

2.1 Study Design – General Aspects

2.1.1 Data Sources

Dataset of patients from Clinical Practice Research Datalink (CPRD) and the Optimum Patient Care Research Database (OPCRD) will be used for analyses.

CPRD¹, formerly known as the General Practice Research Database (GPRD), is a computerised longitudinal research database containing anonymised medical record data from approximately 650 subscribing UK primary care practices.

OPCRD² is a respiratory-enriched primary care research database compiled by Optimum Patient Care providing chronic respiratory review services. It contains anonymous, longitudinal data extracted from over 550 UK practices (>178.000 patients with COPD). It is approved by Trent Multi Centre Research Ethics Committee for clinical research use and offers a high-quality data source that is used regularly in clinical, epidemiological and pharmaceutical research.

Both datasets are constructed separately using data in a patient unidentifiable manner

Sub-study 1 will use patient data extracted from the Optimum Patient Care Research Database (OPCRD). The OPCRd is developed, maintained, and owned by Optimum Patient Care (OPC), a social enterprise company that aims to improve patient outcomes through medical research and services. OPC provides evidence-based recommendations to UK general practices through bespoke software and practice reports.

For sub-studies 2, 3 and 4, data of patients from the Clinical Practice Research Datalink (CPRD) with linkage to HES Admitted Patient Care and HES A&E and outpatient datasets will be used. CPRD data will be extracted through AZ's account.

¹ <https://www.cprd.com>

² See <http://optimumpatientcare.org/opcrd/>

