2.5 Study designs

2.5.1 Objective 1

The index date (ID) of objective 1 will be the most recent date of a recorded blood eosinophil count, measured at the time of stable disease, defined as no COPD exacerbation within 4 weeks prior to or at ID and no change in treatment regimen, ICS dosage and substance during the study period (Figure 1).

[figure not shown]

Figure 2. Study design objective 1

Patient's demographics and clinical characteristics will be described and potential confounders will be assessed in a baseline year prior to ID.

The association between high blood eosinophil counts (at ID) and (moderate or severe) COPD exacerbations in the subsequent year will be assessed in subgroups of patients defined by smoking status (active smoker in baseline year or not) and the following treatments in the baseline year (22):

1. Short-acting bronchodilators as required only (SABA and/or SAMA)
2. Maintenance therapy with LAMA and/or LABA
3. ICS / LABA in combination inhaler
4. Triple therapy: ICS + LABA + LAMA

The primary definition of "high eosinophil counts" will be $\geq 0.45 \times 10^9/L$, based on our previous work. Sensitivity analyses will be performed using 0.25, 0.35 and 0.55 as cut-points.

Sensitivity analyses will be performed in the subgroup of patients with COPD who have never been diagnosed with asthma, i.e., no diagnostic Read code for asthma recorded ever.

Additional analyses will be performed to evaluate whether the Medication Possession Ratio (MPR) for maintenance treatments (ICS / LAMA / LABA) modifies the associations by:

1. Including interaction terms of blood eosinophil counts and MPR into the regression model (continuous or categorical depending on best model fit) to explore whether MPR significantly modifies the association and at which values
2. Repeating analyses in patients with good adherence to ICS, using the widely used cut-point of $MPR \geq 80\%$ for therapy options 3 and 4

2.5.2 Objective 2

The ID of objective 2 will be the date of the most recent first discharge from hospital admission for COPD exacerbation occurring within one year after a blood eosinophil count measured at the time of no recent exacerbation (Figure 3). Patients will be followed after ID until re-admission or death to a maximum of one year after each index date.

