3.6 Sample Size and Power Calculations

3.6.1 Sub-study 1

Figure 6 shows that 1,645 patients are required for each therapy group to find a significant ($\alpha=0.05$) Rate Ratio of 1.3 as previously found with 80% power, when analysing the association between high blood eosinophil counts and the number of exacerbations, assuming 10% of patients having high blood eosinophil counts and mean rate of events of 0.68 in patients without high blood eosinophil counts as previously observed.

Table 2 shows the proportions of COPD patients on different treatment options in a previous study of OPCRD patients with COPD.

Table 2. Frequencies of therapy options in a previous OPCRD study of patients with classical COPD

Therapy option	Frequency (%) in classical COPD patients
SABA and/or SAMA	18
LAMA and / or LABA	11
ICS / LABA combined	17
Triple therapy	14

Around 46,000 COPD patients from OPCRD are estimated to be available for analyses of whom one third is expected to be an active smoker. Thus, 5,000 to 8,000 OPCRD patients are estimated to be available for each treatment group of whom 3,400 to 5,500 are not active smokers.

[figure not shown]

Figure 6. Total sample size (Y-axis) required for finding different Rate Ratio's (X-axis) significant with 80% statistical power, assuming a mean rate of events of 0.68 in patients without high blood eosinophil counts and a prevalence of 10% of high blood eosinophil counts

3.6.2 Sub-study 2

A recent study performed in Scotland found hospital admission rates of 127 per 1,000 patient years for COPD exacerbations at any diagnostic position (24). In that study, 10% of re-admission occurred within 14 days.

Around 10,000 patients with a blood eosinophil count available within one year prior to a hospital admission for COPD recorded in HES are required for finding a hazard ratio of 1.3 significant ($\alpha=0.05$), assuming a baseline re-admission risk of 10% and 10% of patients having high blood eosinophils (Table 3).

Table 3. Numbers needed for finding different Hazard Ratio's

Hazard Ratio high vs normal	Re-admission risk in patients with normal eosinophil counts	Prevalence of high eosinophil count	Total number of COPD patients required	Numbers needed normal / high	Power at $\alpha=0.05$
1.4	10%	10%	5,729	5,161 / 568	80%
1.3	10%	10%	10,079	9,080 / 999	80%
1.2	10%	10%	22,442	20,218 / 2224	80%

3.6.3 Sub-study 3

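### Sub-study 1 tests a cut-point and a smoking-specific hypothesis taken from earlier OPCRD work in OPCRD again, with no rule or supplementary analysis separating patients already analysed

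*Protocol*

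**What the plan says.** Protocol section 1.1 (Background) reports earlier work in "real-life UK patients with COPD from the Optimum Patient Care Research Database (OPCRD) when using a higher cut-point of" 0.45 × 10⁹/L or above, seen in 10% of that population. On smoking it adds: "However, the association was limited to patients who were not actively smoking". On size: "Ex-smokers with high blood eosinophil counts showed a 32% higher rate of exacerbations than ex-smokers with normal eosinophil counts". On treatment: "The association was found in patients treated with ICS and in patients in GOLD groups B to D". That work was submitted but not yet published when the protocol was written.

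These results then reappear as design elements:

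- Section 1.3 (Hypotheses) expects an "increased rate of exacerbations at all levels of treatment in patients who are not actively smoking".
- Section 2.5.1 makes 0.45 the primary cut-point, "based on our previous work. Sensitivity analyses will be performed using 0.25, 0.35 and 0.55 as cut-points".
- Section 3.6.1 plans on a "Rate Ratio of 1.3 as previously found with 80% power".

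Section 2.1.1 then returns to the same database: "Sub-study 1 will use patient data extracted from the Optimum Patient Care Research Database (OPCRD"). It uses CPRD with HES linkage for sub-studies 2 to 4. The inclusion and exclusion criteria (2.3, 2.4) contain nothing that removes, flags or splits off patients from the earlier analysis. The index date in 2.5.1 is each patient's most recent eligible count. None of the four limitations in 3.5.2 mentions reuse of the database.

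**The concern.** A p-value or confidence interval has its usual meaning when the hypothesis was fixed without sight of the outcomes used to test it. Here the cut-point and the smoking stratum of interest were fixed after seeing OPCRD outcomes, and the test goes back to OPCRD. If many of the same patients, with the same counts and outcome years, enter both analyses, part of any chance excess in the earlier result passes into the new rate ratios. A reader of the sub-study 1 report could then take agreement between the two as replication when part of it is the same data counted twice.

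The stake is how the non-smoker rate ratios at 0.45 are read. The arithmetic of the plan is not in question.

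**Working it through.** **1. The plan's own sample size.** Inputs from section 3.6.1: rate 0.68 with normal counts, rate ratio 1.3 (so 0.68 × 1.3 = 0.884), 10% with high counts, 80% power, α = 0.05 (two-sided assumed). With a square-root Poisson comparison:

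N = (1.960 + 0.842)² × (1/0.10 + 1/0.90) / [4 × (√0.884 − √0.68)²] ≈ 1,632.

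This is within 1% of the stated 1,645, so that figure is sound as a Poisson calculation.

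**2. Pooled re-test, no selection step.** Assume no true association and an earlier result with z > 1.96. Assume too that shared patients keep the same exposure and outcome windows. If two equal-sized samples share a fraction f, their z-statistics have correlation f. If one sample is wholly contained in the other and makes up a fraction f of it, the correlation is √f. The quantity wanted is P(both z > 1.96) / 0.025.

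| Shared fraction | Equal-sized samples | One nested in the other |
|---|---|---|
| 0 | 2.5% | 2.5% |
| 25% | 7.9% | 18.5% |
| 50% | 18.5% | 34% |
| 75% | 38% | 53% |
| 90% | 59% | 70% |

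At full overlap the answer is 100% by definition, because it is the same analysis of the same data. It carries no information.

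**3. One regimen fully inside the earlier sample.** If the regimen makes up a share s of that sample, the correlation is √s. With the shares in Table 2 (11%, 14%, 17%, 18%), assumed to hold in non-smokers, the probabilities are 10.6%, 12.3%, 14.0% and 14.6%.

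**4. Allowing for a chosen cut-point and stratum.** As an illustration, suppose the earlier result was the best of four cut-points in two smoking strata. Assumed prevalences are 35%, 20%, 10% and 5%; only the 10% is in the protocol. The null correlation between nested cut-points with prevalences a > b is √[b(1−a) / (a(1−b))]. In 1,000,000 simulated null data sets, 14.1% had a best z above 1.96. Among these:

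- the pooled re-test is positive in 2.6% with no overlap, 19% with half overlap of equal-sized samples, and 35% with half overlap and nesting;
- with full overlap and four equal regimens, any given regimen is positive in 19%;
- all four regimens are positive together in fewer than 0.01%.

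Steps 2 to 4 give the two ranges: about 11–19% for one fully nested regimen and about 18–35% for a pooled re-test with half overlap.

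**5. Room to separate patients.** Section 3.6.1 expects 3,400 to 5,500 non-smokers per regimen. On the Poisson figure, 1 − 1,645/3,400 = 52% of the smallest group and 1 − 1,645/5,500 = 70% of the largest could be set aside. The planned model is negative binomial, and no dispersion is stated. With dispersion k = 1 (an assumption), a Wald calculation gives

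N = (2.802)² × [(1/0.884 + 1)/0.10 + (1/0.68 + 1)/0.90] / (ln 1.3)² ≈ 2,744.

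The smallest group could then lose only 1 − 2,744/3,400 = 19%. At 1,645 patients, power would be about 58%.

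**The case against.** The case on the other side is substantial.

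- **The protocol claims no independent confirmation.** Section 1.2 takes the earlier association as found and asks about the role of treatment, naming ICS-adherent patients and triple therapy as unknown. Asking new subgroup questions where a main effect was seen is ordinary extension work. This stands.
- **Overlap is inferred.** The size, period and selection rules of the earlier cohort are not given. Sub-study 1 also requires unchanged therapy across baseline and outcome years, and a more recent count gives a different outcome year. This stands, and it is why only ranges can be shown. The same group, the same database and a paper still under submission make some overlap likely but do not measure it.
- **Smoking limits the hypothesis, not the analysis.** Active smokers form their own stratum (2.5.1), and three other cut-points are run. This is correct, but those analyses use the same database and do not restore independence.
- **Planning on an earlier effect is normal.** Agreed: 1.3 is a planning value and is no fault in itself.
- **There is outside support.** Section 1.1 cites a Danish cohort with higher risks above 0.34 × 10⁹/L, so a strict null is pessimistic. It is used here for illustration only.

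A reader might infer that a positive result at every treatment level is close to guaranteed. The documents do not support that: even in the null model with full overlap, all four regimens are positive together in fewer than 0.01% of runs.

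**Conclusion.** The point holds in a limited form. The cut-point and the non-smoker hypothesis come from OPCRD and are tested in OPCRD, and nothing in the protocol separates or discloses the shared patients. To an unknown extent, the rate ratios in non-smokers at 0.45 are therefore not independent of the data that suggested them. The ranges in the working rest on a null effect, an earlier significant result, assumed overlap fractions and identical windows for shared patients. If the earlier sample was large, optimism in the size of the effect is small, and what is lost is mainly the claim to independent evidence.

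It would go too far to say that sub-study 1 is mere repetition, or that the non-overlapping patients must become the primary analysis set. The regimen and adherence questions are new, and giving up sample size for independence in the primary analysis is a debatable trade. What remains is a cheap improvement in analysis and reporting.

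**What to change.** Keep the full OPCRD analysis as primary and make three additions.

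1. In 3.4.1, add a supplementary analysis that fits the same regimen- and smoking-specific models at ≥0.45 × 10⁹/L in patients not included in the earlier OPCRD analysis, where they can be identified.
2. If they cannot be identified, or too few remain, fit the same models in the CPRD-HES cohort already planned for sub-studies 2 to 4. Use the most-recent-count index date of sub-studies 3 and 4, and apply the stable-therapy criterion of sub-study 1.
3. In 3.5.2, state the possible overlap with the earlier work, and in the report describe results in overlapping patients as an extension or re-analysis.

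The cost is one more run of the same models, with wider intervals. OPCRD records are anonymised and the protocol describes no identifier linking successive extracts, so the patient flag may not be feasible; the CPRD route covers that case. The non-overlapping set may have less than 80% power under negative binomial dispersion, so it should be read by its estimates and intervals. The two databases are built separately without patient identifiers, so possible overlap of practices between them should be acknowledged. The CPRD run should be included in the ISAC application that section 4.1.1 schedules at protocol sign-off.
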